1.7 Therefore, sample size will be calculated taking into account

a. Assumption on expected effects declared in the main efficacy criterion;

1.8 calculation of sample size for two-sided test for the final analysis will be made using the formula:

$$n = \frac{\left(z_{\alpha/2} + z_{\beta}\right)^2}{(b - \delta)^2 p_1 p_2 d}$$

where **n** – total sample size of the product and placebo, **p**₁ – proportion of subjects from the total sample size in Anaferon for children group, **p**₂ – proportion of subjects from the total sample size in placebo group, **p**1=**p**2=**0.5**); **b** – effect size (calculated as **b** = **ln**(**T**₁/**T**₂)). δ – minimum clinically relevant effect δ =**ln**(1+ Δ /**T**₂); **z**_{α /2} and **z**_{β} – relevant tabular values of z-test; **d** – expected proportion of subjects reaching primary endpoint during the study.

1.9 Final sample size will be determined using the formula:

$$\mathbf{N}_{\mathrm{F}} = \mathbf{N}_{\mathrm{PP}} / (1 - \mathbf{K}_{\mathrm{B}}),$$

where N_F – final sample size; N_{PP} – result of calculation in cl. 1.8, i.e. scheduled number of children completing the study per protocol; K_B – withdrawal coefficient.

2. Assumptions on expected clinical study effects.

CONFIDENTIAL

It was initially suggested that in Anaferon for children group proportion of subjects falling ill with ARVI/influenza in 12 weeks (84 days) after the treatment onset will not exceed 65%, in placebo group will be at least 80% (conservative estimate based on the study), therefore the difference between the study arms will be less than 15%. Minimum clinically relevant difference between the groups will be 5%.

However, due to essential inability to obtain complete data on all the disease cases in all the subjects enrolled during the study (data censored, right) and necessity to determine typical time to the disease development, we will reformulate the condition on effects in the assumption of exponentially distributed disease cases:

$P_i=1-exp(-\lambda_i T),$

where P_i – proportion of ill subjects in I group, λ_i – risk of disease in I group, T – followup time.

Therefore, evaluation of risk for experimental groups is defined as

$$\lambda_i = \ln(1-P_i)/(-T),$$

median time to the event

$T_{1/2,i}=ln(2)/\lambda_i$

At that the expected median time to the disease in placebo group is **36** days, minimum clinically relevant difference is **6** days (therefore, minimum median time for superiority is **42** days). The scheduled effect is equal to **19** days (median time to the disease in Anaferon for children group is **55** days).

Thus, the intended effect in terms of Cox model will be $\mathbf{b} = \ln(56/36) = \ln(1.53) = 0.425$, minimum clinical effect will be $\delta = \ln(42/36) = 0.154$. Based on the assumptions on the effects we will also take the presumed total proportion of subjects falling ill during the study as equal to $\mathbf{d} = 0.725$. Therefore, sufficient number of influenza/ARVI cases required to reject null hypothesis is 437, the total required number of subjects (PP) is 604 (accurate value 602.75).

As the subject recruitment covers more than one epidemic season, **blind interim analysis** will be made in each season to assess nuisance parameters of the study.

According to the above mentioned statistical terms and assumptions, sample size of each group for the final analysis will be **302** subjects for each group (PP set is **604** in total).

Given potential withdrawal of at least **15%** of the subjects at the screening and during the study for various reasons, at least **355** subjects should be enrolled in each group (**710** subjects in total, see 1.9).

Interim analysis

The analysis is made in accordance with point 2 without unblinding the treatment group.

CONFIDENTIAL

Statistical criteria

All statistical calculations will be made using the following groups of statistical criteria:

- parametric to assess continuous and interval accidental values;
- non-parametric to obtain:
 - evaluations on equality/inequality of proportions of subjects compared for various visits,
 - analysis of frequencies in features compared, and
 - evaluation of continuous and interval accidental values in case of violation of requirement on normal sample distribution.

Parametric criteria will be checked for normality of the samples compared (Kolmogorov-Smirnov test).

The following *parametric methods and approaches* are suggested:

- To evaluate differences in continuous variables obtained in one group at two different visits – Student t-test for paired samples.
- For evaluation of time changes in parameters under comparison analysis of variance (ANOVA) or covariance (ANCOVA) analysis in a modification with repeated measurements (Repeated Measures).
- 3. In the case of multiple comparisons of groups among themselves, various corrections for multiplicity will be applied (Dunnett, Tukey, Scheffe, adapted Holm criterion, etc).
- 4. For more complex data structures, approaches will be used with the construction of Generalized Linear Models and / or Mixed Linear Models.
- 5. Selection of the type of distribution, refinement of the factor and covariance structures of the model is carried out using fit statistics, such as AIC (Akaike Information Criterion).

To carry out the statistical analysis and approaches specified above the following SAS procedures are suggested:

- UNIVARIATE check for normalcy of distributions compared
- CORR, MEANS calculation of descriptive statistics
- TTEST Student t-test with all modifications
- GLM analysis of general linear models for studying temporal dynamics (ANOVA, ANCOVA)
- GENMOD analysis of generalized linear models
- MIXED mixed linear model analysis
- PHREG survival analysis.

Nonparametric criteria:

Below are the main types of possible comparisons with their respective criteria:

- 1. For evaluation of time changes in parameters under comparison, the Friedman test, a nonparametric analogue of variance analysis with repeated measurements.
- 2. For frequency analysis of contingency tables $2 \times 2 \chi^2$ test (if the frequencies compared exceed 5) of exact Fisher's test (if one of the frequencies compared is < 5).
- 3. For frequency analysis of contingency tables with multiple comparisons Cochran-Mantel-Haenszel test (modification of χ^2 test for multiple comparisons).
- 4. For the frequency analysis of data on the presence / absence of an event or outcome during repeated measurements (contingency tables with dependent strata) survival analysis.

To perform the above-mentioned non-parametric statistical analysis options, it is assumed that the following SAS procedures are used:

- FREQ Friedman test, χ^2 -test and / or Fisher exact test; Cochran–Mantel–Haenszel test
- LIFETEST survival analysis
- NPAR1WAY Mann-Whitney U-test.

Safety parameters

Adverse events recorded during the study will be grouped into frequency tables by severity, seriousness and relationship with the study product.

Data presentation

Descriptive statistics will be provided for each study continuous / interval variable. Numerical data will be presented by mean, standard deviation, min and max values. Comparisons suggesting statistical conclusion will have the relevant confidence intervals. Outliers will be analyzed individually. The data will be grouped by visits. Categorical variables will be presented as frequency tables by visits.

SAS-9.4⁵ software will be used for statistical analysis including various parametric and nonparametric tests.

⁵ Licensee: LLC NPF Materia Medica Holding, №70100045.

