If in the period from 2 to 12 weeks a participant falls ill with influenza/ARVI¹, then he prematurely completes participation in the study (as having reached the primary endpoint). A participant is considered fallen ill with influenza/ARVI if the doctor identifies the following symptoms: febrile/subfebrile body temperature, presence at least one flu-like nonspecific symptom (decreased activity/impaired behavior/weakness; headache; chills) and at least one respiratory symptom (runny nose; nasal stuffiness; hoarseness/husky voice; sore throat; cough). In this case, the doctor makes an unscheduled visit (at home or in a medical center), which is final. During the visit, the doctor carries out the procedures of Visit 4. A nasopharyngeal swab is taken to identify the most common pathogens of influenza/ARVI².

If ARVI/influenza occurs within the first seven days from the onset of preventive therapy, the disease will not be recorded as an adverse event and will not be taken into account to evaluate the efficacy of the study drug, since an early manifestation of influenza/ARVI may indicate that the participant was included in the study when he/she was in the incubation period of an infectious disease.

During the study, concomitant therapy for underlying chronic conditions, as well as routine vaccination of the participant, are allowed, with the exception of the drugs indicated in the section "Prohibited Concomitant Treatment".

Inclusion and exclusion criteria

Inclusion criteria

- 1. Children of either gender aged from 1 month to 6 years old³.
- 2. The absence of clinical symptoms of any infectious disease, but not earlier than 14 days from its onset.
- 3. Seasonal rise in ARVI incidence, confirmed by official information.
- 4. An information sheet (Informed Consent form) for the subject participation in the clinical trial signed by one parent/adopter of the patient.

Exclusion criteria

 Acute or subacute period of infectious disease of any etiology (viral, bacterial, fungal, etc.) and localization (including upper and lower respiratory tract infection, meningitis, sepsis, otitis media, urinary tract infection, intestinal infection, etc.).

¹ The symptoms associated with teething or vaccination (post-vaccination reactions and complications) are not considered as manifestations of influenza/ARVI.

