- The patient's parent/adopter parent works for OOO "NPF "MATERIA MEDICA HOLDING" (i.e., the company's employee, part-time employee under contract or appointed official in charge of the trial, or their immediate family).

Discontinuation criteria

1. Failure or refusal of the child or his/her parents/adopters to comply with the protocol.

⁴ Primary and secondary immunodeficiencies, regardless of etiology, are characterized by persistent immunodeficiency. Transient immunomodulation do not represent immunodeficiency. Children with recurrent respiratory infections have transient immunomodulation. High rates of infectious diseases during the first years of life should not be considered as a pathology; this condition is not attributable to immunodeficiency and does not exhibit negative effect on immunity formation. Such subjects are eligible.

Subjects with immunodeficiency need complex therapy using the products forbidden within the study.

- 2. The necessity to use medications not permitted within the study.
- 3. An adverse event requiring discontinuation of the investigational product.
- 4. The desire of the child or parent/adoptive parent to complete the study ahead of schedule for any reason.
- 5. Cases not specified by the protocol, when the investigator decides that the further participation may harm the child.
- 6. Incorrect inclusion of ineligible child.
- 7. The patient did not pass the screening procedure.
 - 8. The participant got influenza/ARVI.

Number of subjects

1036 participants of both genders aged 1 month to 6 years old (518 participants in each group) are planned to be included and randomized in the clinical trial. It is estimated that approximately 880 children (440 participants in each group) will complete participation in the study in accordance with the protocol.

Interim analysis

Since the recruitment of participants covers more than one epidemic season, a blind intermediate analysis is carried out in each season (without revealing the participant's membership in one or another experimental group) to possibly clarify a priori research parameters.

Based on the results of a blind interim analysis, a significant difference between the base population frequency of the events studied and the planned one will be revealed, the sample size of the study is reassessed.

Treatment

Group 1

Name of the medicinal product: Anaferon for children

Active ingredient: affinity purified antibodies to human interferon-gamma – 0.003 g*

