- pidotimod/imunorix
- interleukins
- synthetic immunostimulants (levamisole, alpha-glutamyl-triptophan/thymogen, etc.)
- thymus hormone-containing drugs
- herbal immunostimulants (immunal[®], etc.)
- 3. Immunosuppressants (L04).
- 4. Antineoplastic agents (L01) and hormones (L02).
- 5. Immune sera and immunoglobulins (J06).
- 6. Fenspiride (R03DX03), omalizumab (R03DX05).
- 7. Systemic corticoids (H02AB).
- 8. Homeopathic drugs.
- 9. Drugs known to cause allergic reactions in the patient.

Study design scheme

Schedule of study procedures

| Procedure/visit | Visit 1 | Visit 2 «phone» | Visit 3 «phone» | Visit 4 |
|-----------------------------------|---------|-----------------|-----------------|------------------|
| | (Day 1) | (Week 4±3 days) | (Week 8±3 days) | (Week 12±3 days) |
| Obtaining signed informed consent | + | | | |

CONFIDENTIAL

Protocol No. MMH-AD-008 23-Aug-2018

| | | | | 20 1148 2010 |
|---|---|---|---|--------------|
| form (ICF) | | | | |
| Eligibility assessment | + | | | |
| Recording concomitant medications | + | + | + | + |
| Randomization and prescription of study therapy | + | | | |
| Study drug supply | + | | | |
| Drug accountability and return, assessment of treatment compliance | | | | + |
| Evaluation of treatment safety | + | + | + | + |
| Telephone survey | | + | + | |
| Collection of nasopharyngeal swabs for PCR diagnosis* | | * Performed in case the child falls ill with influenza/ARVI during unscheduled (additional) visit with Visit 4 procedures | | |

Statistical Analysis

Samples

Statistical analysis will be carried out in the following sets:

Total set includes all participants whose parents/adoptive parents signed the Informed Consent Form.

The sample including all enrolled and randomized subjects who received at least one dose of the study drug to be used for analysis of *safety and tolerability* (*Safety population*), as all adverse events identified after the study product administration were recorded.

Full Analysis Set consists of all enrolled and randomized patients, except for those who met at least one of the following criteria:

- 1) failure to meet inclusion/non-inclusion criteria;
- 2) subject failing to take any dose of the study drug;
- 3) absence of any data on the subject after randomization.

This is the best set for the Intention-to-treat method, so it will be used in the Intention-to-treat efficacy analysis of the test therapy.

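### Adverse events are planned only as frequency tables while observation stops at influenza/ARVI, so crude frequencies by arm rest on unequal time at risk if the drug works

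*Combined protocol and SAP*

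**What the plan says.** Safety is part of the study objective. The section Safety parameters (Statistical Analysis) consists of one sentence: "Adverse events recorded during the study will be grouped into frequency tables by severity, seriousness and relationship with the study product". The Samples section defines the safety population as all randomized children with at least one dose, on the ground that "all adverse events identified after the study product administration were recorded". No person-time denominator, incidence rate or time-to-event method is assigned to adverse events.

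Observation has no common length. Under Study design, a child who falls ill between weeks 2 and 12 "then he prematurely completes participation in the study (as having reached the primary endpoint"). The next step is: "In this case, the doctor makes an unscheduled visit (at home or in a medical center), which is final". Discontinuation criterion 8 repeats the rule: "The participant got influenza/ARVI". No later safety contact is described. For illness in the first seven days, "the disease will not be recorded as an adverse event and will not be taken into account to evaluate the efficacy of the study drug". The plan does not say whether influenza/ARVI after day 7 is recorded as an adverse event.

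Evaluation of sample size, item 2, gives the expected illness, Anaferon first: "subjects falling ill with ARVI/influenza in 12 weeks (84 days) after the treatment onset will not exceed 65%, in placebo group will be at least" (the placebo figure is 80%). It then states that "we will reformulate the condition on effects in the assumption of exponentially distributed disease cases".

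**The concern.** The event that ends observation is the primary efficacy event. If the drug delays illness, its arm stays under observation longer and has more opportunity to report adverse events, even when the underlying rates are identical. A child who leaves in week 3 counts in the denominator exactly as a child observed for 84 days.

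In a placebo-controlled trial the adverse-event tables will be read by arm. The safety half of the objective would then be answered by a comparison that mixes tolerability with efficacy.

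**Working it through.** **Inputs.** From Evaluation of sample size: illness by day 84 of 65% (Anaferon) and 80% (placebo), exponential times, T = 84 days. From Number of subjects: 518 randomized per arm. Adverse-event risks are not in the documents; 10%, 20% and 30% over a full 84 days are assumptions. Withdrawal for other reasons is ignored.

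**1. The plan's own event model.** λ = −ln(1−P)/84 gives −ln(0.35)/84 = 0.01250 per day on Anaferon and −ln(0.20)/84 = 0.01916 on placebo. Medians ln 2/λ are 55.5 and 36.2 days (plan: 55 and 36). The mean proportion ill is (0.65 + 0.80)/2 = 0.725, as stated. With the plan's b = 0.425 and δ = 0.154, the formula gives 427.5 events and 427.5/0.725 = 589.6 children, within about 3% of the stated 437 and 604. The model is therefore the plan's own.

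**2. Mean observation time.** With follow-up cut at illness or day 84, the mean is P/λ:
- Anaferon: 0.65/0.01250 = 52.0 days
- Placebo: 0.80/0.01916 = 41.8 days
- Ratio 1.25, or about 73.8 versus 59.2 person-years in 518 children per arm

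**3. How the ratio moves.**

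| Scenario | Observation ratio |
|---|---|
| 65% vs 80% ill (plan) | 1.25 |
| Same, but illness ends follow-up only after day 7 (56.4 vs 47.3 days) | 1.19 |
| 70% vs 80% | 1.17 |
| 75% vs 80% | 1.09 |
| No effect (80% vs 80%) | 1.00 |
| Plan's hazard ratio 0.652, placebo illness 40% | 1.09 |
| Plan's hazard ratio 0.652, placebo illness 20% | 1.04 |

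**4. Crude adverse-event percentage, same constant hazard h in both arms.** With h = −ln(1−risk)/84, the percentage is h/(h+λ) × [1 − exp(−84(h+λ))].

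| Assumed 84-day risk | Anaferon | Placebo | Ratio |
|---|---|---|---|
| 10% | 6.2% | 5.0% | 1.24 |
| 20% | 12.6% | 10.2% | 1.23 |
| 30% | 19.1% | 15.6% | 1.23 |

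At the 10% risk, a true adverse-event rate ratio of 0.80 in the drug's favour would appear as a crude ratio of 1.00.

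**5. Early events instead of a constant hazard.** If all adverse events arise in the first 7, 14 or 28 days (10% risk assumed), the crude ratio is only 1.02, 1.05 or 1.09.

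**6. Person-time rates alone.** In the 14-day case the risks are identical and the crude ratio is 1.05. Dividing by total observation gives 1.045/1.246 = 0.84, which falsely favours the drug.

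**7. If endpoint illness were counted as an adverse event.** At the 20% risk, the chance of an adverse event or illness by day 84 is 1 − 0.35 × 0.80 = 72% on Anaferon and 1 − 0.20 × 0.80 = 84% on placebo. Removing first-week illness (at most 1 − 0.35^(1/12) = 8.4 and 1 − 0.20^(1/12) = 12.6 points) lowers both figures but does not change the order. The crude imbalance would then run against placebo.

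**The case against.** The strongest reply is that the plan promises tables and not a comparison. It names no between-arm test for adverse events and does not say that percentages will be shown. A reader might infer from the chi-square and Fisher tests listed for 2×2 tables that adverse-event percentages will be formally tested; the text does not say so. This stands as a limit on wording. Descriptive figures by arm carry the same distortion.

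The general methods also contain tools that could help. Nonparametric criteria, item 4, points to survival analysis for the presence or absence of an event over repeated measurements, and PHREG and LIFETEST are listed. None of these is tied to adverse events, and the safety section names only frequency tables.

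Data presentation groups categorical data by visit. If each 4-week table used the children still on study at its start, observation within a window would differ by about 1.09 (23.6 versus 21.7 days). Those denominators are not stated, so this is possible but not planned. The document also calls itself a protocol summary, so silence here is weaker evidence than silence in a full SAP.

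Finally, the ratio of 1.25 needs the full planned effect, and the 23–24% inflation also needs a constant adverse-event hazard. Both limits stand.

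**Conclusion.** The point holds as a gap worth closing. As written, crude frequencies by arm would rest on observation times that depend on the primary outcome. Under the plan's assumptions the observation ratio is 1.25, or 1.19 if first-week illness does not end follow-up. It falls to 1.09–1.17 for smaller effects and vanishes with no effect. The resulting inflation of crude percentages on the drug is about 23–24% with constant hazards and about 2–9% if events come in the first 7 to 28 days. The adverse-event risks behind the displayed percentages are assumptions; the ratio hardly depends on them.

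Two stronger readings are not supported:
- **That the tables will necessarily show an excess on the drug.** The plan leaves open whether influenza/ARVI after day 7 is an adverse event. If it is, the direction can reverse.
- **That the tables would conceal harm from the drug.** With endpoint illness left out and the planned effect present, the distortion works against the active arm and tends to overstate harm.

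**What to change.** - Keep the frequency tables.
- Report observation time by arm.
- State whether influenza/ARVI after day 7 is recorded as an adverse event. Leave endpoint illness out of the comparative adverse-event tables, or show it on separate lines.
- For any between-arm safety statement, use time to first adverse event: cumulative incidence by arm and a hazard ratio with 95% CI, censored at the end of observation. PHREG and LIFETEST are already listed. Illness should be handled as censoring; treating it as a competing event would bring back the crude proportion. State the assumption that this censoring is unrelated to adverse-event risk.
- Give incidence per 100 child-weeks as a supportive summary only, with its constant-hazard assumption stated. Used alone it can mislead, as step 6 of the working shows.

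The cost is a small amount of programming, plus adverse-event onset and final-visit dates. The documents do not say that last-dose dates are recorded, so the final visit is the safer end point for observation time. Visits, treatment and sample size are unaffected. The choice should be fixed before unblinding.
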